July 2018	
Intervention assignment: Individuals that had activated a MyChart Bedside account prior to the study start or in a Full-Tech unit were manually assigned to the Full-Tech intervention regardless of their MRN. Individuals who were found to have accessed both Full and Lite versions over the course of the study were excluded from the analysis for this study.
	
Quality assurance testing of ongoing data collection of the MyChart Bedside usage data revealed that patients who were to have been assigned to Lite-Tech based on their MRN were, in fact, using functions only available on Full-Tech. Subsequent review also found the reverse to be true, participants that were assigned to Full-Tech were limiting their usage to those functions in Lite-Tech.
 
The study team conferred with Epic—the electronic health record (EHR) vendor that developed the code to assign patients to a particular arm of Tech status—and manually reconstructed Tech assignment using the original assignment code. A cohort of individuals were identified as not having received the intended Tech assignment. Through this process, the study team was able to secure the true Tech intervention status. Individuals that had activated a MyChart Bedside account or were in a Full-Tech unit prior to the study start were manually assigned to Full-Tech regardless of their MRN. Additionally, individuals who were found to have accessed both Full and Lite versions over the course of the study were identified and subsequently excluded from the analysis for this study. This scenario may have occurred when a patient was assigned an MRN at admission but subsequent records review identified an existing MRN. In these cases, individuals unexpectedly transitioned between two Tech intervention states.

Section 4.2.1		

Section 2: Introduction

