3.1.3 Allocation ratio

The Tech intervention contrasted two function sets—Lite-Tech (40% allocation), which was a minimalistic toolset focused on providing basic data to the patient, and Full-Tech (60% allocation), a more expansive toolset. The Touch intervention contrasted two training approaches—Low-Touch, a self-guided approach where patients could view built-in tutorials, and High-Touch (initially 50% allocation), where patients receive in-person guided training with the technology. The realized allocation ratios are presented in Table 2.

Table 2. Realized allocation ratio.

Tech Allocation	Touch Allocation		Total
	High	Low	
Full			
Frequency	624	1,523	2,147
Row %	29.1%	70.9%	100.0%
Column %	69.3%	76.5%	74.2%
Overall %	21.6%	52.7%	74.2%
Lite			
Frequency	277	468	745
Row %	37.2%	62.8%	100.0%
Column %	30.7%	23.5%	25.8%
Overall %	9.6%	16.2%	25.8%
Total			
Frequency	901	1,991	2,892
Row %	31.2%	68.8%	100.0%
Column %	100.0%	100.0%	100.0%
Overall %	31.1%	68.8%	100.0%

The assignment protocol used three phases where the Touch allocation ratio was changed by the research team.

1. In Phase 1, patients received the High-Touch intervention only after consenting to the study and submitting their Admission survey (see Section 3.8.2). Low-Touch patients could view the tutorial at any point and were not required to complete the Admission survey. Phase 1 assigned patients to High/Low-Touch in a 1:1 ratio.
2. In Phase 2, beginning in February 2018, the study shifted to a 3:1 ratio of High/Low-Touch. This change was done to ensure that sufficient individuals were assigned to the High-Touch intervention due to under-enrollment. Quality monitoring of the study found a number of exogenous factors that were impacting the High-Touch intervention, including, but not limited to: patient discharges; patient moved to other rooms; patient not present during TN rounding; patient was engaged with the care team and unable to work with the TN; and tablet returned prior to receiving an intervention. This change in the ratio was intended to increase the number of patients who would be eligible to receive a High-Touch intervention while maintaining the *per protocol* approach in that these exceptions were considered a component of the Protocol.

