3.2.1 Tech randomization

Tech randomization was accomplished using a 4-digit random number table generated using Stata version 14.0 which was used as a comparison table against the last four digits of the patient's Medical Record Number (MRN) which was assigned prior to study assignment. A preliminary simulation analysis found that random assignment using this model created appropriately sized groups of 40% and 60%.

Individuals who had access to the Full version of MyChart Bedside prior to enrollment in the study (i.e., those patients who were admitted to the Cancer Center, which was not included as a site, or patients who had used MyChart Bedside during the pilot phase of implementation in which only Full-Tech was available) maintained their Full-Tech status and were excluded from randomization if they were transferred to a unit included in the study.

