4.2 Adherence and protocol deviations

The HT2 study was designed as a pragmatic study with the interventions conducted using a *per protocol* approach.

Protocol deviations

Protocol deviations may have occurred if:

1. a participant consented to participate in the study but subsequently requested a change in Tech status to the OSUWMC;
2. a participant was admitted to the OSUWMC, was assigned to the Lite intervention, and was subsequently admitted to a unit that always received the Full version of MyChart Bedside.

In these cases, the individual was removed from the study.

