4.2.1 Operational protocol amendments

Operational protocol amendment 1: Improve enrollment yield (Jan 2017)

A research team member could visit the patient to remind them to complete the survey, limited to three visits per patient, once per day. Patients without completed surveys could also be visited on subsequent hospital admissions to complete their survey.

Operational protocol amendment 2: Improve data quality (Jul 2017)

A confirmation was added to each page of the survey to inform respondents when they had left questions unanswered on a page. They could continue to advance if that was their preference.

Operational protocol amendment 3: Intervention available after consent (Feb 2018)

TNs were allowed to make first contact for the High-Touch intervention once the patient consented—no longer waiting for a complete Admission survey. The TN should work with the patient to walk them through completing the survey during the intervention.

Operational protocol amendment 4: Intervention assignment (Mar 2018)

Individuals that had activated a MyChart Bedside account or were in a Full-Tech unit prior to the study start were manually assigned Full-Tech regardless of their MRN.

Individuals who were found to have accessed both Full and Lite versions over the course of the study were to be excluded from the analysis for this study.

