6.3.1 Multiple MRNs

MRNs were used as primary identifiers by both the hospital and in the context of the study. Moreover, MRNs were used throughout data processing to associate data with a unique patient. Typically, each unique patient had a single, unique MRN. In rare cases, for instance when a patient presented in the emergency room and was unable to provide identification, a patient may have been temporarily issued an MRN. While hospital records are adjusted to ensure a single, unique MRN at a later time, data was written to the log files with the temporary MRN. Patients with multiple MRNs were identified, along with their duplicate MRNs, and the identifiers were recoded to a “primary” MRN in the processed data.

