### 1.4 Assumptions and testing

#### 1.4.1 Analysis populations

Estimates of the intervention effects were calculated on two analytic populations. The main analytic population of the study used an *intention-to-treat (ITT)* approach. Using this paradigm, participants were analyzed on the basis of the study group to which they were randomized, regardless of their eventual receipt of that intervention.

The effects of the intervention were additionally evaluated on a *per-protocol* population, composed exclusively by those participants who were administered their randomized intervention. The analysis of the data from the per-protocol population was weighted by the inverse of their probability to receive the intervention to which they were originally randomized, computed on the basis of the following demographic and clinical characteristics: sex, race, age at time of enrollment, Charlson Comorbidity Index, length of stay.

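### The protocol removes participants after assignment for using both portal versions, asking to switch, or entering an always-Full unit, so the SAP's main Tech analysis is not intention-to-treat

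*Protocol*

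**What the plan says.** **Main population.** SAP 1.4.1 names ITT as the main analytic population, in which "participants were analyzed on the basis of the study group to which they were randomized, regardless of their eventual receipt of that intervention". A weighted per-protocol population is additional. SAP 1.2 says that all available data were used. The SAP neither lists nor revokes any exclusion for crossover between Tech versions, and SAP 1.4.5 refers to the final protocol, so the two are meant to be read together.

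**Removals.** Protocol 4.2 lists two deviations that lead to removal from the study:
- Item 1: "a participant consented to participate in the study but subsequently requested a change in Tech status to the OSUWMC".
- Item 2: a participant assigned to Lite who later enters a unit that always runs the Full version.

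Protocol 4.2.1, amendment 4, adds that individuals found to have "accessed both Full and Lite versions over the course of the study were to be excluded from the analysis for this study". Protocol 1.8 offers a possible cause: "This scenario may have occurred when a patient was assigned an MRN at admission but subsequent records review identified an existing MRN".

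**Related text.** Protocol 4.3 calls the analytic population per protocol. Protocol 3.1.3 and 3.2.1 set Tech from the last four MRN digits, at 40% Lite and 60% Full. SAP 1.5.1 counts inpatient portal sessions in the enrollment admission only.

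**The concern.** ITT protects the comparison because nothing that happens after assignment decides who is counted. Here, three post-assignment events decide it. Two concern which version a patient came to have, and one concerns which version a patient wanted.

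The both-versions rule raises a further problem for H1, where portal use is the outcome. A patient can be flagged only if use was logged under each version, so the exclusion is tied to the thing being measured.

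The Tech contrast serves both primary hypotheses, H1 and H2. If removals differ by arm and the people removed differ in use or satisfaction, the Full versus Lite comparison is biased, and the label ITT would hide this. The SAP's inverse-probability weights do not help: they apply only to the per-protocol set, and people removed beforehand are in neither set.

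**Working it through.** **1. Reproduce Table 2 (Protocol 3.1.3).** Lite 745/2,892 = 25.8%; Full 2,147/2,892 = 74.2%. Both agree with the table.

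**2. Compare each removal with the ITT rule.**

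| Removal | Triggered by | Arms it can affect |
|---|---|---|
| Both versions accessed (4.2.1) | Logged use under each version, at any time in the study | Both |
| Change of Tech requested (4.2, item 1) | Preference after consent | Both; direction not stated |
| Later entry to an always-Full unit (4.2, item 2) | Version received | Lite only |

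None is compatible with analysis by randomised group regardless of receipt. The third is arm-dependent by construction and needs no assumption.

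**3. Time window.** The H1 session count covers the enrollment admission (SAP 1.5.1). The inpatient use data cover each visit in the study period (Protocol 6.2), and the both-versions rule covers the whole study. As worded, it can drop a patient whose enrollment admission was entirely under one version because of use at a later admission.

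**4. Removal rates on the MRN route.** Assume that the second MRN is an independent draw at the planned split, and that use was logged under both versions whenever the two draws differ.
- P(second draw is Full | Lite) = 0.60
- P(second draw is Lite | Full) = 0.40
- Rate ratio: 0.60/0.40 = 1.5
- Expected counts, as a share of changed-MRN patients: Lite 0.40 × 0.60 = 24%; Full 0.60 × 0.40 = 24%

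The higher Lite figure is therefore a rate within arm, not a larger number of people. Let m be the share of patients with a changed MRN (not given; assumed). Lite loses 0.6m and Full loses 0.4m:
- m = 1%: 0.6% and 0.4%
- m = 5%: 3.0% and 2.0%
- m = 10%: 6.0% and 4.0%

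**5. Add the always-Full rule.** If it removes a further 2% of Lite (assumed) at m = 5%, Lite loses 1 − 0.97 × 0.98 = 4.9% and Full still loses 2.0%.

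**6. Possible effect on the use ratio.** Suppose that there is no true Tech effect and that changed-MRN patients use the portal k times as much as others (k assumed).
- Lite mean = [(1 − m) + 0.4mk] / [(1 − m) + 0.4m]
- Full mean = [(1 − m) + 0.6mk] / [(1 − m) + 0.6m]

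At m = 10% and k = 3: Lite 1.02/0.94 = 1.085, Full 1.08/0.96 = 1.125, ratio 1.037.

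| m | Full/Lite, k = 2 | Full/Lite, k = 3 |
|---|---|---|
| 1% | 1.002 | 1.004 |
| 2% | 1.004 | 1.008 |
| 5% | 1.010 | 1.019 |
| 10% | 1.019 | 1.037 |

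At k = 1 the ratio is 1.000. At k = 0.5 and m = 2% it is 0.984/0.988 = 0.9960 for Lite and 0.986/0.992 = 0.9940 for Full, a ratio of 0.998. The sign depends on k.

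**7. Can the MRN route explain Table 2?** No. Even at m = 100% the Lite share would be 0.4 × 0.4 / (0.4 × 0.4 + 0.6 × 0.6) = 0.16/0.52 = 30.8%, still above 25.8%.

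**The case against.** The strongest reply is that these exclusions fit the per-protocol framework of Protocol 4.2 and 4.3, and that the real conflict is Protocol 4.3 against SAP 1.4.1. On that view the exclusions are only a consequence. They are indeed part of that conflict, but changing the population label in 4.3 would leave 4.2 and 4.2.1 in force, so they need their own correction. It could also be said that the SAP, by listing no exclusions, overrides the protocol. Neither document says so.

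Several stronger conclusions are tempting and are not supported:
- **That the rules raise the Full/Lite use ratio.** Being flagged needs one logged access under each version, not heavy use. The protocol's example of a temporary MRN, an emergency patient who could not give identification, does not suggest a heavy user.
- **That the 60:40 split makes every route fall harder on Lite.** The split bears only on the MRN route, which Protocol 1.8 gives as something that may have occurred. The direction of requested switches is not stated.
- **That patients were in fact dropped for later admissions.** The wording allows it; no text shows that it happened.
- **That the Tech arm was wrongly rebuilt from recoded MRNs.** Protocol 6.3.1 says "Patients with multiple MRNs were identified, along with their duplicate MRNs" and recodes them to a primary MRN in the processed data. It does not say that Tech was taken from that number, and Protocol 1.8 says that the true Tech status was secured.
- **That the 25.8% Lite share measures these removals.** Patients with earlier Full access were placed in Full outside randomisation, other exclusions applied, and step 7 rules out the MRN route as the explanation.
- **That the number excluded is unreported.** The CONSORT figure was not available for this check and may give it.

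**Conclusion.** The concern holds as a conflict between the documents and as an opening for arm-dependent selection. With the three removals in force, the main Tech analysis is not ITT as SAP 1.4.1 defines it, however many people are involved. The always-Full rule certainly acts on Lite alone. The both-versions rule conditions on logged use and may reach beyond the admission on which the H1 session count is based. It removes changed-MRN patients at 1.5 times the rate in Lite only if the second MRN is an independent 60:40 draw with use under both.

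The size and direction of the bias are unknown. From the MRN route alone it is probably small: Protocol 6.3.1 calls multiple MRNs rare, and at m of 1% to 2% the illustrated ratio stays within 1% of 1, even with threefold use. The amounts contributed by switch requests and by the always-Full rule cannot be judged from the text. No effect on H2 has been quantified.

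**What to change.** 1. In the main ITT analysis, keep all three groups (both-versions users, change-requesters, and Lite patients who entered an always-Full unit) in the Tech arm originally assigned by the MRN-based code at the enrollment admission.
2. Handle patients placed in Full without randomisation (Protocol 3.2.1 and amendment 4 in 4.2.1) separately from the randomised Tech comparison. They have no randomised Tech arm, and applying the code to their MRN could put them in Lite.
3. Use the three exclusions only in the per-protocol or a sensitivity analysis.
4. Report the number excluded by assigned arm and by reason.
5. Reconcile Protocol 4.2, 4.2.1 and 4.3 with SAP 1.4.1.

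The cost is revised wording and a re-run. Protocol 1.8 says that Tech assignment was already reconstructed with the vendor using the original code, and Protocol 6.3.1 says that the log files carry the temporary MRN. The downside is that a few crossovers will slightly dilute the Tech effect.

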4.3 Analysis populations

The analytic population of the study used a *per protocol* approach. Using this paradigm, study participants assigned to the High-Touch group that did not receive the High-Touch intervention were reassigned to the Low-Touch group. In rare instances (n=3) where a patient was assigned to the Low-Touch group but received the training intervention due to patient request, they were reassigned to the High-Touch group.

Section 5: Trial population

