3.1.2 Intervention description: Touch - High/Low

The education and training intervention, referred to as Touch, was performed by trained Technology Navigators (TNs) who deliver training tailored to both the version of

ⁱ This function was automatic, so was not considered selectable and not included in the count of functions for either the Full- or Lite-Tech versions.

MyChart Bedside installed on their tablet (both Full- and Lite-Tech) and the perceived capacity of the patient.

Patients assigned to the Low-Touch intervention received an intervention focused on providing them with resources to conduct self-guided learning of MyChart Bedside. Specifically, TNs directed patients to the tutorial videos integrated in the MyChart Bedside application that explained the portal's functions.

In contrast, patients assigned to the High-Touch intervention would systematically review each of the functions of MyChart Bedside with the TN who would discuss how and when they are appropriately used. Patients were encouraged to use their tablet and follow along with the training as the TN moved through each function and ask the TN questions about their records during the presentation. The TNs tailored their presentation based on a patient's demonstrated knowledge of the technology to minimize patient participation burden while focusing on explaining the value of each function within the application. Patients unavailable after three intervention attempts were converted to Low-Touch.

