**Section 2: Changes to the Statistical Analysis Plan**

The original statistical analysis plan was specified based on assumptions about the data collection and distributions of the data, and was designed to be exploratory and flexible to account for violation of modeling assumptions. The final statistical analysis plan reflects a more detailed description of how the analyses were performed.

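### Protocol 4.3 analyses Touch by training received, SAP 1.4.1 by randomised group; neither withdraws the other, and the place of never-randomised patients in the Tech contrast is left open

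*Protocol*

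**What the plan says.** **Touch, Protocol.** Section 4.3 says that the analytic population follows a per protocol approach, under which "study participants assigned to the High-Touch group that did not receive the High-Touch intervention were reassigned to the Low-Touch group". Three Low-Touch patients who asked for and received training move the other way. Section 3.1.2 has the same conversion as an operating rule: "Patients unavailable after three intervention attempts were converted to Low-Touch". Section 3.1.3 says that the change of ratio kept the per protocol approach.

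**Touch, SAP.** Section 1.4.1 makes ITT the main population: "participants were analyzed on the basis of the study group to which they were randomized, regardless of their eventual receipt of that intervention". It adds a per-protocol population "composed exclusively by those participants who were administered their randomized intervention", weighted by the inverse probability of receiving the randomised intervention. Non-recipients are left out of that set, not moved.

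**Which document governs.** The nearest statement is in SAP Section 2: "The final statistical analysis plan reflects a more detailed description of how the analyses were performed". Neither that section nor the revision table in Protocol 1.8 mentions a change of analysis population.

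**Allocation.** Phase 1 was 1:1; then, "beginning in February 2018, the study shifted to a 3:1 ratio of High/Low-Touch". Phase 3 kept 3:1. On the outcome of this, Protocol 3.1.3 says: "The realized allocation ratios are presented in Table 2".

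**Tech.** Protocol 3.2.1 says that patients with earlier access to the Full version kept it and were not randomised. Protocol 4.2.1 (amendment 4) and 1.8 (July 2018) assign such patients to Full-Tech by hand whatever their MRN, and exclude from analysis those who used both versions. The SAP does not mention patients without a Tech randomisation.

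**The concern.** Two different main populations for Touch stand on file, and per protocol has two meanings: move non-recipients in the Protocol, leave them out and weight in the SAP.

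The choice matters because being trained was not random. Protocol 3.1.3 lists why training failed: discharge, a room move, absence during rounds, being with the care team, or returning the tablet. In Phase 1, moreover, "patients received the High-Touch intervention only after consenting to the study and submitting their Admission survey". Each of these can plausibly be related to portal use, satisfaction or self-efficacy. Under 4.3, High-Touch holds only patients who could be trained, and Low-Touch collects all who could not, from both randomised arms. The difference between the groups then mixes the effect of training with the difference between these kinds of patient. Most models offer little protection: the SAP lists no covariates for H1, the involvement outcomes of H2, adoption under H3a, or H4.

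On Tech, a population defined by randomised group has no evident place for patients who were never randomised. If they are analysed as Full-Tech, the Tech contrast is partly non-randomised, and these patients had earlier experience of the product.

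**Working it through.** **1. Reproduce Table 2 (Protocol 3.1.3).** Cells: Full/High 624, Full/Low 1,523, Lite/High 277, Lite/Low 468; total 2,892. High = 624 + 277 = 901, and 901/2,892 = 31.2%. Low = 1,991. Full = 2,147, and 2,147/2,892 = 74.2%. The table reproduces.

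**2. Is Table 2 compatible with the randomised Touch groups?** The lowest planned High share is 50%, or 1,446 patients. z = (901 - 1,446)/sqrt(2,892 x 0.25) = -545/26.9 = -20.3. Chance is ruled out. Without regrouping, at least 1,991 - 901 = 1,090 more High than Low patients would have to have been excluded. Section 4.3 supplies the simpler explanation: the table is grouped by receipt.

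**3. How many were moved?** Assume that exclusions were even across arms and that the 3 Low-to-High patients are among the 901, so 901 - 3 = 898 were trained as randomised. Let f be the share of enrolment at 3:1 (not given).

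- Assigned High: A = 2,892 x (0.50 + 0.25f)
- Moved to Low: M = A - 898
- Untrained share of High: u = M/A

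If the untrainable share is also u among those randomised to Low, all 2,892u untrainable patients end in the Low group of 1,991. Let d be the mean outcome of trainable minus untrainable patients. With no Touch effect, the 4.3 grouping shows d x 2,892u/1,991.

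| f | A | M | M/1,991 | Spurious High minus Low |
|---|---|---|---|---|
| 0 (bound) | 1,446 | 548 | 28% | 0.55d |
| 0.1 | 1,518 | 620 | 31% | 0.59d |
| 0.3 | 1,663 | 765 | 38% | 0.67d |
| 0.5 | 1,808 | 910 | 46% | 0.73d |
| 1 (bound) | 2,169 | 1,271 | 64% | 0.85d |

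Both ratios were used, so the true value lies strictly between the bounds. For f = 0.3: u = 765/1,663 = 0.46, and 0.46 x 2,892/1,991 = 0.67.

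The documents do not give d. As an illustration only, d = 5 points would give 3.0 to 3.7 points for f from 0.1 to 0.5. Protocol 3.4 says the design was to detect changes of 2.2% to 3.8%.

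**4. Phase under ITT.** With f = 0.3, the share of High enrolled at 3:1 is 0.75 x 0.3/0.575 = 0.39, and of Low 0.25 x 0.3/0.425 = 0.18. An ITT model without phase would carry 0.39 - 0.18 = 0.21 of any outcome change between the two periods. No such change is shown.

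**5. Tech.** Planned Full share 60%, or 1,735 patients. z = (2,147 - 1,735.2)/sqrt(2,892 x 0.24) = 411.8/26.3 = 15.6. This is consistent with never-randomised patients counted as Full, but it does not isolate them. Let L and F be the Lite and Full patients removed beyond an even rate. The never-randomised number is then 2,147 - 1.5 x (745 + L) + F = 1,029.5 - 1.5L + F. Neither L nor F is given, so the number cannot be identified.

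**The case against.** **The SAP already settles it.** SAP 1.4.1 is explicit, and Section 2 presents the final SAP as the fuller account of what was done. A reader might infer from 4.3 that the reported Touch results are as-treated; the documents do not support that. If the results follow the SAP, the Touch part is mainly a matter of wording. This stands, but 4.3 is still in force on paper and Table 2 appears to follow it.

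**The size rests on assumptions.** True: f, d and even exclusions are all assumed, and d may have either sign. No bias in any named outcome is demonstrated. Figure 1 is not shown in the available copy and may give the randomised counts.

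**Patients with prior Full access are covered by a rule.** They are: Protocol 1.8, 3.2.1 and 4.2.1 label them Full-Tech. Only their place in the ITT Tech contrast is open. Setting L = F = 0 in step 5 tempts one to report about 1,030 such patients. That is neither an estimate nor a ceiling, because Protocol 4.2 and 4.2.1 provide for removals that can fall on either Tech arm.

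**The survey dates look contradictory but are not.** Protocol 4.2.1 dates the easing of the survey requirement to February 2018 and 3.1.3 to March. Protocol 1.8 describes two steps, 22 days apart, which explains both.

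**ITT does not cure everything.** Protocol 6.3.8 drops patients with no portal use during the enrolment admission. That exclusion comes after assignment and can depend on training, so its selection remains under ITT.

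**Conclusion.** The contradiction on Touch is real and should be resolved: two main populations, two meanings of per protocol, and no available text that withdraws 4.3. Confidence is high. Following 4.3 would carry selection into the Touch contrast. Under even exclusions, the patients moved to Low number more than 548 and fewer than 1,271; with 30% of enrolment at 3:1 they are about 765 (38% of Low), and the spurious contrast is about 0.67d. This also assumes the same untrainable share in both randomised arms.

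The Tech part is narrower and of medium confidence. The label for patients with prior Full access is given; whether they belong in the ITT Tech contrast is not. The Full share of 74.2% against 60% is consistent with their inclusion, but their number is unknown.

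**What to change.** 1. State in both documents that ITT as defined in SAP 1.4.1 is primary for Touch. Relabel the 4.3 grouping as an as-treated secondary analysis, so that per protocol means only the SAP's weighted set. Section 3.1.2 can stay as a record of delivery.
2. Restrict the main Tech and Tech-by-Touch contrasts (SAP Equation 1) to MRN-randomised patients. Apply prior Full access as a baseline exclusion whatever the MRN, so that it falls on both arms alike. Put never-randomised patients in a sensitivity analysis or in the Touch comparison within Full-Tech (Equation 2).
3. Add an indicator for allocation phase to the Touch models, because the ratio changed. This is a safeguard, not the correction of a shown error.
4. Report counts by randomised arm and phase, including patients moved, never randomised and removed, or point to Figure 1 if it gives them.
5. Say that the non-use exclusion in 6.3.8 acts after assignment and is not removed by ITT.

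**Cost.** Wording in both documents. If the results already follow the SAP, the Touch models need only a re-run with phase; otherwise they need a full re-run. Touch assignments were generated at randomisation (Protocol 3.2.2), and Tech assignment has been reconstructed (Protocol 1.8). The Tech sample shrinks by an unknown number. The Touch ITT estimate may be smaller than the as-treated one: with f = 0.3, only 898/1,663 = 54% of those randomised to High were trained.
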